9.2.2.4. Incidents submission

The Manufacturer is responsible to assess if a SAE meets the criteria for Incident reporting. If the SAE meets the criteria for Incident Reporting, the Manufacturer will observe all reporting requirements to the Competent Authority and the Notified Body in conformance with the applicable

DermIng S.r.l., Clinical Research and Bioengineering Institute
[name]
[contact]— www.derming.com
Test code

E0222

law (European directives 93/42/CEE and 90/385/CE reviewed for directive 2007/47/CE) without delay according to MEDDEV 2.12-1 guideline timelines:

- Serious public health threat: immediately (without any delay that could not be justified) but not later than 2 calendar days after awareness by the Manufacturer of this threat.
- Death or unanticipated serious deterioration in state of health: immediately (without any
 delay that could not be justified) after the Manufacturer established a link between the device
 and the event but not later than 10 elapsed calendar days following the date of awareness of
 the event.
- Others: immediately (without any delay that could not be justified) after the Manufacturer established a link between the device and the event but not later than 15 elapsed calendar days following the date of awareness of the event

9.2.3. Adverse event follow up

All SAEs should be followed-up by the Investigator in order to elucidate as completely and practically as possible their nature and/or causality until resolution of all queries, clinical recovery is complete, laboratory results have returned to normal, stable condition is reached or the subject is lost to follow-up.

If the study product causes an adverse event, the Investigator could withdraw the subject from the study. During the final visit the Investigator will determine whether the adverse event is ongoing or resolved. In any case it must be followed up to complete resolution.

The Investigator could decide to momentarily suspend the treatment and then to reintroduce it, only if the subject agrees and if the adverse event has been classified "mild/moderate" and its relationship to the study product results unlikely/possible.

All further follow up visits necessary to monitor the adverse event, will be recorded in the adverse event form.

9.2.4. Occurrence of Pregnancy

The investigator must immediately, at the latest within 24 hours from the investigator first notice of the event, inform the Sponsor of the pregnancy using specific form.

Women who become pregnant during the study will be withdrawn from the study but followed until the outcome of the pregnancy is known, and reported to the Sponsor (baby health) using a pregnancy outcome form.

10. SCHEDULE OF STUDY PROCEDURE

10.1. Baseline (T0)

The visit includes:

- detailed explanation of the study procedures and informed consent signature
- filling in the CRF (personal data, subject's history, concomitant medications)
- check of inclusion/exclusion criteria, with particular attention to the assessment of a possible subject's sensitivity to the test product or its ingredients
- clinical and instrumental assessments
- Profilometry measurement
- 1st micro-injection procedure.

DermIng S.r.l., Clinical Research and Bioengineering Institute	
[name]	
[contact]- www.derming.com	
Test code	22 //
E0222	

10.2. Intermediate visit (T1 1 month after the 1st aesthetic procedure)

The visit includes:

- record of possible adverse events or intervened illness
- clinical and instrumental assessments
- Profilometry measurement
- 2nd injection procedure.

10.3. Final visit (T2, 4 months after the 1st aesthetic procedure)

The visit includes:

- record of possible adverse events or intervened illness
- clinical and instrumental assessments
- Profilometry measurement
- self assessment questionnaire at T2

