4.1. Study plan

Open clinical trial, conducted by 1 center under dermatological control.

3 visits will be performed during the study:

- T0 (baseline) clinical and instrumental evaluations, followed by the 1st injection procedure
- T1 (1 month after the 1st injection procedure) clinical and instrumental evaluations, followed by the 2nd injection procedure
- T2 (3 months after the 2nd injection procedure) clinical and instrumental evaluations.

DermIng S.r.l., Clinical Research and Bioengineering Institute [name] [contact]– www.derming.com

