8.4. Self assessment questionnaire (subjects' judgment)

At T2 each volunteer fills a questionnaire regarding:

- the efficacy of the study treatment on acne scars (score: very marked; marked; medium; light; absent);
- the treatment tolerance (score: bad; poor; medium, good; excellent).

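### The plan does not require the volunteer questionnaire to be completed before the T2 assessments, and its single tolerance score covers two procedures carried out 3 and 4 months earlier

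*Combined protocol and SAP*

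**What the plan says.** Section 1 makes the volunteers' satisfaction with the treatment effects an additional aim. The only listed instrument for it is the questionnaire in section 8.4: "At T2 each volunteer fills a questionnaire regarding" two things. The first is "the efficacy of the study treatment on acne scars (score: very marked; marked; medium; light; absent)". The second is "the treatment tolerance (score: bad; poor; medium, good; excellent)".

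Section 10.3 puts the questionnaire fourth of four items at the final visit, as "self assessment questionnaire at T2". It follows the adverse event record, the clinical and instrumental assessments, and profilometry. The visit lists for T0 (10.1) and T1 (10.2) contain no questionnaire. Section 10.4 gives the premature-end visit the same content as the final visit.

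Section 4.1 describes an open study and sets the timing: "T1 (1 month after the 1st injection procedure) clinical and instrumental evaluations, followed by the 2nd injection procedure", then "T2 (3 months after the 2nd injection procedure) clinical and instrumental evaluations".

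Tolerance has other sources. Section 9.1 counts expected local reactions (swelling, pain, erythema, bruise) and any other adverse event. Sections 10.2 and 10.3 each include a "record of possible adverse events or intervened illness". Section 12.2 defines the analysed sample as those who completed the study in line with the protocol.

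**The concern.** Two separate weaknesses affect the same short questionnaire.

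The first is order. If the volunteer answers after the grading, the efficacy answer may reflect what the physician said or showed as well as the volunteer's own view. With no blinding and no comparator described, the plan offers no other protection for that answer.

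The second is timing and coverage of the tolerance item. Pain, swelling, redness and bruising are reactions to an injection, yet the volunteer first rates tolerance months later, with one score for both procedures. A score of poor would not show which procedure was poorly tolerated. A volunteer who leaves after T1 and attends no further visit gives no score at all, and poor tolerance could be the reason for leaving.

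At stake are the credibility of the volunteer-satisfaction aim and the usefulness of the tolerance self-rating. Neither can be repaired once the data have been collected.

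**Working it through.** **Order.** The three visit lists, side by side:

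| Visit | Section | Items in listed order | Self-rating |
|---|---|---|---|
| T0 | 10.1 | consent, CRF, criteria, assessments, profilometry, 1st injection | none |
| T1 | 10.2 | adverse events, assessments, profilometry, 2nd injection | none |
| T2 | 10.3 | adverse events, assessments, profilometry, questionnaire | efficacy and tolerance |

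The T0 and T1 lists end with the injection, which agrees with the sequence in section 4.1. A site would naturally read the T2 list the same way and hand out the questionnaire last. But no section says that list order is the order of conduct, and none says the questionnaire comes before or after the grading. Photographs are not a separate item in 10.3; the digital images section only says they are taken at each evaluation time. What can be established is that the order is not fixed, and that the natural reading is the less favourable one.

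**Timing.** The inputs are the intervals in section 4.1: 1 month from 1st to 2nd injection and 3 months from 2nd injection to T2.

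- 1 + 3 = 4 months from 1st injection to T2. This reproduces the plan's own figure in the title of 10.3: "Final visit (T2, 4 months after the 1st aesthetic procedure)".
- In weeks: section 4.2 gives 4 weeks between the injections; 3 months × 52/12 = 13 weeks; 4 + 13 = 17 weeks.

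| Source of tolerance information | Look-back, 1st procedure | Look-back, 2nd procedure |
|---|---|---|
| Self-rating as planned (T2 only) | about 17 weeks | about 13 weeks |
| Adverse event record at the next scheduled visit | about 4 weeks (T1) | about 13 weeks (T2) |
| Self-rating with an added T1 item | about 4 weeks | about 13 weeks |

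A T1 item shortens recall for the first procedure by 17 − 4 = 13 weeks. It does nothing for the second, because no visit is scheduled between T1 and T2.

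**Missing ratings.** Section 5.2 gives 30 subjects; the documents give no dropout rate, so the following is an assumption with a range. If k subjects attend T1 and no later visit, the share without any tolerance self-rating is k/30:

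- k = 0: 0%
- k = 1: 1/30 = 3.3%
- k = 3: 3/30 = 10%
- k = 6: 6/30 = 20%

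With a T1 item, each of these subjects would have a rating for the first procedure. An early leaver who does attend the premature-end visit would fill in the questionnaire under 10.4, but section 12.2 may still keep that rating out of the analysis.

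**The case against.** The strongest reply has four parts.

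- **The influence is not documented.** Section 10.3 only says what the visit includes. Nothing says volunteers are told the grade or shown pictures, and section 4.2 says results are worked up after the clinical phase. The Primos section describes what the software can compare, not a display to subjects. This stands. A reader might infer that the volunteer rates efficacy after seeing the grade, photographs and Primos comparison, so that independence is lost. The documents support only that nothing prevents this.
- **Other measures exist.** A reader might infer that the self-rating is the only efficacy view that could be independent of the investigator. It is not, since profilometry does not rest on the investigator's grade. Moreover, volunteers in an open study know they were treated, so expectation remains whatever the order. Reordering brings a modest gain.
- **Recall does not affect both ratings equally.** Tolerance is wholly retrospective. Efficacy is judged on the scars as they are at T2, against a remembered baseline. The long-recall point therefore belongs mainly to tolerance.
- **Tolerance is captured elsewhere.** Adverse events are recorded at T1 and T2, with severity and causality, so the records can partly separate the two procedures. The premature-end visit includes the questionnaire, and section 9.2.2.2 encourages withdrawn subjects to attend. This also stands in part. But these records are not the volunteer's own rating, they do not shorten recall for the second procedure, and section 12.2 may set aside what early leavers provide.

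**Conclusion.** The point holds as a modest measurement weakness that is cheap to correct. The plan does not protect the efficacy self-rating from influence at T2. Its only tolerance self-rating is one score for two procedures, given about 13 and about 17 weeks after them. No stated figure or planned test changes, and the instrument serves an additional aim.

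The intervals come directly from the plan. The direction and size of any influence cannot be estimated from the documents. The share of missing ratings depends on an assumed number of losses after T1. It would be wrong to conclude that tolerance goes unmeasured in those who leave early, because adverse event recording at T1 covers the first procedure for everyone who attends that visit.

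**What to change.** - **Sections 8.4, 10.3 and 10.4:** state that the volunteer completes the questionnaire alone, as the first item of the visit, before any assessment and before being shown any image.
- **Section 10.2:** add the tolerance item at T1, completed before the 2nd injection and referring to the 1st procedure.
- **Sections 8.4 and 10.3:** keep the overall tolerance item at T2 and add one referring to the 2nd procedure, answered only by those who received it.
- **Section 12:** report the T1 tolerance ratings for all who attend T1, whether or not they complete the study, as a stated exception to the completers-only sample in 12.2.

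The cost is a changed order at T2, one or two extra questions and a slightly longer T1 visit, with no added visit. The 2nd procedure would still be rated about 13 weeks afterwards, and the report should acknowledge this as a limit.

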10.4. Premature end of the study

This visit is identical to the final visit.

11. PREMATURE END OF THE STUDY/ END OF THE STUDY

11.1. Withdrawal criteria

Any person who in the course of the trial:

- decides to withdraw the consent for any reason
- does not present to the study visits
- does not comply with the treatment
- develops any of the conditions specified in the original exclusion criteria
- contracts a serious illness that does not allow the study continuation
- other reason of the patient to quit.

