5.4.2. Dependent on a clinical condition

5.4.2.1. Dermatological disease

- Dermatitis;
- presence of cutaneous disease on the tested area, different from those under study
- recurrent facial/labial herpes;
- clinical and significant skin condition on the test area (e.g. active eczema, psoriasis, severe rosacea, scleroderma, local infections and severe acne).

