9.2.2.2 AEs/Incidents reporting procedure

All incidents and adverse events (AEs) or adverse device effect (ADE) regardless the seriousness must be reported in the source file (if applicable) and in the "Adverse event form" (see "CRF" enclosed in Appendices section). Investigators are responsible for documenting adverse events in the eCRF section created for this purpose.

Moreover, the investigator must determine:

- (a) if the event is serious or not
- (b) if the event is related or not related to the study treatment.

Any adverse event, related or not related to the study treatment, must be documented and will be followed until completed resolution (see paragraph 8.2.3.).

Then, the investigator will decide to:

(a) interrupt definitively the study treatment

DermIng S.r.l., Clinical Research and Bioengineering Institute
[name]
 [contact]- www.derming.com
Test code
E0222

² USADE: is an effect which by its nature, incidence, severity or outcome has not been identified in the current version of the IFU /

- (b) continue the study as protocol directed
- (c) interrupt temporary the study treatment
- (d) end the study

In case a subject's withdraws from the trial, the form "End of Study" should be filled in and the reasons for discontinuation recorded. The withdrawal subject should be encouraged to attend the final visit for the last study assessment.

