12.2. Population description

This sample includes all subjects that completed the study according to the protocol.

DermIng S.r.l., Clinical Research and Bioengineering Institute [name] [contact]– www.derming.com

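### A skin condition arising at the injected site is a withdrawal criterion under 11.1 but is left to the investigator under 9.2.2.2 and 9.2.3, and under 12.2 that choice can decide whether the subject is analysed

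*Combined protocol and SAP*

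**What the plan says.** All references are to the combined protocol and SAP.

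- **11.1, Withdrawal criteria.** The list includes anyone who "develops any of the conditions specified in the original exclusion criteria". The bullet is not limited by cause or severity. The next bullet, on serious illness, applies only where the illness prevents continuation.
- **5.4.2.1, Dermatological disease.** The conditions include dermatitis (no limit of site or severity), "presence of cutaneous disease on the tested area, different from those under study", and "clinical and significant skin condition on the test area (e.g. active eczema, psoriasis, severe rosacea, scleroderma, local infections and severe acne").
- **9.2.2.2, AEs/Incidents reporting procedure.** Once an adverse event is documented, "Then, the investigator will decide to" take one of four courses: stop treatment for good, "continue the study as protocol directed", pause treatment, or end the study. A subject who withdraws is to be encouraged to come back for the final visit.
- **9.2.3, Adverse event follow up.** "If the study product causes an adverse event, the Investigator could withdraw the subject from the study". Restarting treatment after a pause is limited to mild or moderate events judged unlikely or possibly related. In every case the event is followed until it has resolved.
- **10.3 and 10.4.** T2 falls 4 months after the first procedure. The premature-end visit has the same content as T2 but no stated date.
- **12.2, Population description.** "This sample includes all subjects that completed the study according to the protocol". No other analysis population is defined, for efficacy or for tolerance.

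**The concern.** The treatment works a needle or cannula back and forth in facial skin and then injects product (4.2). A local infection or dermatitis at that site could come from the procedure. It would then be both an exclusion condition arising on study, which points to 11.1, and an adverse event, which points to 9.2.2.2 and 9.2.3. The first lists it as grounds for withdrawal. The other two make the outcome a matter of judgement.

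The statistical stake comes from 12.2. With only one sample, made up of per-protocol completers, a withdrawal for such an event takes the subject out of the T2 Goodman and Baron grade and Primos results. The reason for leaving is then an event on the treated skin that the treatment may have caused. In an open, single-arm trial of 30 there is no comparator in which similar losses might offset this. Membership of the only efficacy sample may therefore be related to outcome, and may turn on which section the investigator applied.

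**Working it through.** **Step 1: one event, two rules.** Take a local infection at an injected site found at T1.

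| Section | Is it covered? | What follows |
|---|---|---|
| 11.1 with 5.4.2.1 | Yes: local infection on the test area is named | Listed as a withdrawal criterion |
| 9.2.2.2 | Yes: 9.2.1 counts procedure-related events as adverse events | Investigator chooses among four courses, one of which is to continue |
| 9.2.3 | Yes, if the product caused it | Investigator may withdraw the subject |

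No section states an order of precedence or carves out exclusion conditions from 9.2.2.2. By contrast, 9.2.4 settles the matter for pregnancy: withdrawal, with follow-up to outcome.

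**Step 2: what differs between the routes.**

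| | Withdrawn under 11.1 | Continued under 9.2.2.2 |
|---|---|---|
| Follow-up of the event | To resolution | To resolution |
| T2 assessment | Encouraged, not scheduled; undated premature-end visit | Scheduled at 4 months |
| New events up to T2 | Captured only if the subject returns | Captured at T2 |
| In the 12.2 sample | Not clearly, even if T2 is attended | Probably, unless continuing is itself read as a breach of 11.1 |

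**Step 3: scale.** The documents give 30 subjects (5.2) and no event rate, effect size or standard deviation, so there is no figure of the plan to reproduce. Assume k = 1, 2 or 3 of 30 are excluded, a mean change of 1 (arbitrary unit, improvement positive) in the others, and a true change d in those excluded.

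Full-sample mean = ((30 − k) × 1 + k × d) / 30. Completers' mean = 1. Inflation = 1 / full-sample mean − 1.

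| k | d = 1 | d = 0 | d = −1 |
|---|---|---|---|
| 1 | 0% | 30/29 − 1 = 3.4% | 30/28 − 1 = 7.1% |
| 2 | 0% | 30/28 − 1 = 7.1% | 30/26 − 1 = 15.4% |
| 3 | 0% | 30/27 − 1 = 11.1% | 30/24 − 1 = 25.0% |

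The column d = 1 shows that there is no bias if the event is unrelated to scar outcome.

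**Step 4: how likely is at least one such event?** With an assumed risk p per subject, the chance is 1 − (1 − p)^30: 46% for p = 2%, 79% for p = 5%, 96% for p = 10%.

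**Step 5: precision is a minor matter.** For a paired t-test with two-sided alpha 0.05 and 80% power (both assumed), the detectable standardised change is 0.53 with 30 subjects and 0.56 with 27. The issue is selection, not loss of power.

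**The case against.** - **11.1 may not be mandatory.** Its lead-in has no main verb. It could be a list of grounds for considering withdrawal, which agrees with 9.2.3, or a specific rule overriding the general adverse-event rules. Either reading would remove the conflict. The documents state neither, and 9.2.3 could equally be called the specific rule for product-caused events. A reader might infer that 11.1 compels withdrawal; the text does not go that far.
- **Observation does not simply stop.** A reader might infer that the event has two different ends of follow-up, or that a subject withdrawn at T1 loses 3 of the 4 planned months of safety observation. The documents do not support this as a general statement. The event is followed to resolution on both routes, return for the final visit is encouraged, and 10.4 provides a visit with T2 content. The loss applies only to new events, and only if the subject does not return.
- **There is one analysis sample.** A reader might infer two analysis sets. Section 12.2 defines one, and what is uncertain is membership. A subject continued despite 11.1 might be ruled out as well. This stands, but it does not help the plan: a subject with a full T2 assessment could then be left out.
- **Such events may be rare.** The expected local reactions in 9.1 (swelling, pain, erythema, bruising) are not named in 5.4.2.1, and the 8 subjects treated beforehand had no adverse events (section 3). This stands: the frequency is unknown.
- **A tolerance event is not a poor scar result.** This also stands. Nothing in the documents links infection or dermatitis to a change of 0 or −1, so the direction of bias is plausible, not shown.

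**Conclusion.** The point holds in a limited form. Sections 11.1, 9.2.2.2 and 9.2.3 treat the same skin event differently without saying which governs, and 12.2 makes that choice bear on who is analysed. At risk are the T2 efficacy assessment on its scheduled date, the capture of new events up to T2, and the subject's place in the only analysis sample. Follow-up of the event itself is not at risk.

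Each such subject is 1 of 30, or 3.3% of enrolment. The inflation of 3.4% to 11.1% rests wholly on the assumed count (1 to 3) and the assumed change of 0. A reader might take the 25.0% cell as the expected bias, but it needs three excluded subjects who all worsened by as much as the others improved, and the documents support no such figure. The ambiguity is worth correcting before analysis because it is cheap to remove and the excluded subjects may not be a random subset.

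**What to change.** 1. **Reconcile the rules.** The sponsor should reconcile 11.1, 9.2.2.2 and 9.2.3 so that it is clear which governs an exclusion condition arising after T0 and recorded as an adverse event. This review takes no position on which withdrawal or treatment rule is right.
2. **Amend 12.2, whichever rule is kept.** Include all treated subjects with a baseline and any post-baseline assessment in the change-from-T0 summary, and all treated subjects in the tolerance summary. Keep the completers as a supportive set.
3. **Use visits already in the plan.** For withdrawn subjects who consent, use the final-visit assessment that 9.2.2.2 already encourages, at the scheduled T2 date. The premature-end visit (10.4) is the fallback, with its actual timing shown.
4. **Leave pregnancy under 9.2.4.** It is also listed among the exclusion criteria (5.4.1) and has its own rule, so the new wording should not reach it.

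The cost is a few sentences in 11.1 and 12.2 and cross-references in 9.2.2.2 and 9.2.3, with no new visit type or procedure. The downside is that a few subjects with incomplete treatment are included, and the mean change may look slightly less favourable.
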